9.3.1.2 Dose Reduction Criterion

- **Apixaban:**

- The recommended dose of apixaban is 2.5 mg taken orally twice daily in patients with NVAF and at least two of the following characteristics: age \geq 80 years, body weight \leq 60 kg, or serum creatinine \geq 1.5 mg/dL (133 micromole/L).
- NVAF patients with severe renal impairment (creatinine clearance 15-29 mL/min) patients should receive the lower dose of apixaban 2.5 mg twice daily for the prevention of stroke and systemic embolism.

- **Rivaroxaban:**

- In patients with moderate (creatinine clearance 30 - 49 ml/min) or severe (creatinine clearance 15 - 29 ml/min) renal impairment, the recommended dose is 15 mg once daily for the prevention of stroke and systemic embolism in patients with non-valvular atrial fibrillation.

- **Warfarin:**

- Warfarin itself does not have dose-reduction requirements however the dose needs to be titrated to maintain INR between 2.0-3.0. In this study, we would not use the dose adjusting criterion for warfarin as it is variable and difficult to take in to account.

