9.3.3 Covariate definition

The following variables will be collected among the three study cohorts (apixaban, rivaroxaban and warfarin) both at start and index date (the date among cases and controls):

- Age and sex distribution at start date/index date
- Naïve/Non-Naïve at index date: Use of OAC other than the index OAC before index date
- Frailty: we will estimate an electronic frailty index (eFI) at start date/index date by using an algorithm developed and validated in THIN (Clegg et al. 2016). Briefly the eFI score is simply an equally weighted calculation of deficits present out of the total 36 deficits identified. Patients will be classified into four mutually exclusive categories based on this score: a) Fit = 0-0.12, b) Mild frailty = 0.12-0.24, c) Moderate frailty = 0.24-0.36, and d) Severe frailty = >0.36.
- Renal disease: estimated glomerular filtration rate (eGFR) before start date/index date will be calculated using the formula described in Table S1 (Annex 3). In prior studies we found that eGFR could not be estimated in less than 5% of AF patients. ACR (Albumin/Creatinine Ratio) will also be ascertained.
- Comorbidity: history of haemorrhagic disease and history of intracranial haemorrhage, urogenital bleeding and gastrointestinal bleeding. Liver disease, pancreatic disease, cancer, cardiovascular disease (acute MI, coronary artery disease, congestive heart failure, ventricular arrhythmia, peripheral arterial disease) cardiovascular risk factors (hypertension, diabetes mellitus, hyperlipidaemia and obesity), stroke/TIA, respiratory disease (asthma and chronic obstructive pulmonary disease), rheumatoid arthritis, osteoarthritis, gastrointestinal disease, liver disease and pancreatic, alcohol-related disorders before start date/index date.
- CHADS2 (0-6) and CHA₂DS₂Vasc (0-9) scores will be calculated at start and index date based on the presence/ history of congestive heart failure, hypertension, age, diabetes mellitus and prior stroke or transient ischaemic attack. HAS-BLED (0-9) score for major bleeding risk (hypertension, renal disease, liver disease, stroke history, prior major bleeding or predisposition to bleeding, age > 65, medication usage predisposing to bleeding, alcohol usage history), will also be calculated. Numbers and proportion will be calculated per value.
- Smoking status, body mass index (BMI) and Townsend score: most recently recorded value before the start date/index date.

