controls” in such a way that the frequency of matching factors (age categories, sex, and calendar year) among selected controls at their random dates matches that of the cases at the index date (i.e. frequency-matched controls). In other words, if 2% of cases are males, belong to the age category 40-49 and have 2010 as year of their index date, then 2% of controls are males, belong to the age category 40-49 and have 2010 as year of their random date. Under our study design of incidence density sampling, the odds ratio (OR) is an unbiased estimator of the incidence rate ratio (RR) (Rothman 2012). Unconditional logistic regression models will be used to obtain OR estimates of OAC use adjusted by baseline variables described above and OAC use at index date. The model will include all covariates described in section 9.3.3 in the logistic regression model (fully-adjusted model). Additionally, and depending on the number of cases ascertained, we could explore simpler models based on either change-in-estimate or statistical significance approaches. Specifically the following analyses will be performed for each outcome:

- a) OAC daily dose: We will use the daily dose criteria described in 9.3.1.2 to classify current users of rivaroxaban and apixaban and compare with warfarin as follows:

Rivaroxaban

- Overall Rivaroxaban (both doses) vs warfarin
 - o 20mg OD – No dose reduc. criteria – Appropriate vs warfarin
 - o 20mg OD – Dose reduction criteria – Inappropriate vs warfarin
 - o 15mg OD - No dose reduc. criteria – Inappropriate vs warfarin
 - o 15mg OD – Dose reduction criteria – Appropriate vs warfarin
 - o Overall Appropriate use vs warfarin

Apixaban

- o Overall Apixaban (both doses) vs warfarin
 - 5mg Bid - No dose reduc. criteria – Appropriate vs warfarin
 - o 5mg Bid – Dose reduction criteria – Inappropriate vs warfarin
 - o 2.5mg Bid - No dose reduc. criteria – Inappropriate vs warfarin
 - o 2.5mg Bid – Dose reduction criteria – Appropriate vs warfarin
 - o Overall Appropriate use vs warfarin
- b) Outcomes will also be analysed in the sub-group of diabetes and by renal function (CKD-EPI) (creatinine clearance or serum creatinine as described in the label of the respective NOAC). Since renal function is taken into account in this classification, individuals without

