Annex 3: Additional information

List of Read Codes

Table S1:
Operational definitions for subpopulations:

Non-valvular Atrial Fibrillation (NVAf)	Patients with a record of Atrial fibrillation (AF) any time prior index date or within the 2 weeks after the index date, and free of valvular replacement or mitral stenosis (see table codes below) prior to index date or 2 weeks after index-date
Renal Impairment	We will obtain eGFR values from creatinine values (AHD code 1400019) using the CDK-EPI* formula. Furthermore we will define four levels of decreasing severity of Renal impairment (CKD-EPI) eGFR >50 mL/min eGFR 30–49 mL/min eGFR 15–29 mL/min eGFR <15 mL/min Unknown -

***CDK-EPI Formula:** $eGFR = 141 * \min(Scr/\kappa, 1)^\alpha * \max(Scr/\kappa, 1) - 1.209 * 0.993^{Age} * 1.018$ [if female] * 1.159 [if black]

Scr: serum creatinine (mg/dL)

κ : 0.7 for females and 0.9 for males

α : 0.329 for females and 0.411 for males

min : the minimum of Scr/ κ or 1

max : the maximum of Scr/ κ or 1.

Table S3- AF READ codes

READ	Description
3272.00	Ecg: atrial fibrillation
3273.00	Ecg: atrial flutter
3274.00	Ecg: paroxysmal atrial tachy.
7936A00	Implant intravenous pacemaker for atrial fibrillation
G570.00	Paroxysmal supraventricular tachycardia
G570000	Paroxysmal atrial tachycardia
G573.00	Atrial fibrillation and flutter
G573000	Atrial fibrillation
G573100	Atrial flutter
G573200	Paroxysmal atrial fibrillation
G573z00	Atrial fibrillation and flutter nos

14AN.00	H/o: atrial fibrillation
212R.00	Atrial fibrillation resolved
662S.00	Atrial fibrillation monitoring
6A9..00	Atrial fibrillation annual review
9hF..00	Exception reporting: atrial fibrillation quality indicators
9hF1.00	Excepted from atrial fibrillation qual indic: Inform dissent
9Os..00	Atrial fibrillation monitoring administration
9Os0.00	Atrial fibrillation monitoring first letter
9Os1.00	Atrial fibrillation monitoring second letter
9Os2.00	Atrial fibrillation monitoring third letter
9Os3.00	Atrial fibrillation monitoring verbal invite
9Os4.00	Atrial fibrillation monitoring telephone invite
G573300	Non-rheumatic atrial fibrillation

Table s4 READ Codes for mitral stenosis (to exclude from AF patients)

READ	Description
G11..11	Rheumatic mitral valve disease
G110.00	Mitral stenosis
G110.11	Rheumatic mitral stenosis
G112.00	Mitral stenosis with insufficiency
G112.12	Mitral stenosis with incompetence
G112.13	Mitral stenosis with regurgitation
G113.00	Nonrheumatic mitral valve stenosis

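### The rivaroxaban dose criterion is stated in creatinine clearance, the only renal formula given is CKD-EPI eGFR, and the protocol does not settle which of them classifies appropriate and inappropriate use

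*Protocol*

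**What the plan says.** **Criteria (Protocol 9.3.1.2).** Rivaroxaban has a single criterion, in clearance: "In patients with moderate (creatinine clearance 30 - 49 ml/min) or severe (creatinine clearance 15 - 29 ml/min) renal impairment". Apixaban has two routes. One needs "at least two of the following characteristics" (age, body weight, serum creatinine). The other is "severe renal impairment (creatinine clearance 15-29 mL/min").

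**Use of the criteria (9.7(a)).** "We will use the daily dose criteria described in 9.3.1.2 to classify current users of rivaroxaban and apixaban". The resulting dose-by-criterion cells, each compared with warfarin, carry both primary objectives in section 8.1.

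**Renal measure (9.3.3 and Annex 3, Table S1).** Renal disease enters as eGFR, which "will be calculated using the formula described in Table S1 (Annex 3"). Table S1 says: "We will obtain eGFR values from creatinine values (AHD code 1400019) using the CDK-EPI* formula". The formula uses creatinine, age, sex and race, and the result is cut at 50, 30 and 15 mL/min.

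**Where the two meet (9.7(b)).** Outcomes are to be analysed "by renal function (CKD-EPI) (creatinine clearance or serum creatinine as described in the label of the respective NOAC"). No clearance formula is given. The text goes on to exclude patients without renal function values, expected to be under 5%, because renal function enters the classification.

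**Body size (9.3.3).** BMI is listed; body weight is not.

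**The concern.** The primary exposure depends on whether each patient meets a renal criterion, and the protocol points to two different quantities for deciding this. CKD-EPI eGFR and creatinine clearance diverge with age and weight. Cutting eGFR at 50, 30 and 15 does not reproduce clearance cut at the same values.

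If eGFR is used, the consequences differ by drug. For rivaroxaban the renal measure is the whole criterion. For apixaban it decides only the second route, because the first uses age, weight and serum creatinine directly. The study's hypothesis (section 7) is that reduced dosing without an apparent indication is more common with apixaban (about 30%) than with rivaroxaban (about 10%), and that this shows in stroke rates. A rule that misplaces mainly rivaroxaban users disturbs that contrast. The limitations in 9.9 attribute exposure misclassification to prescriptions not captured in the database and do not mention the renal measure.

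**Working it through.** The protocol gives no figure for this point, so there is none to reproduce.

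**Step 1. Which measure does the text imply?** Read literally, 9.7(a) applies the 9.3.1.2 criteria, hence clearance. Three details point to eGFR instead:
- CKD-EPI is the only renal formula.
- The under-5% missing figure in 9.7 matches the share of patients in whom 9.3.3 says eGFR could not be estimated. A weight-based clearance would also lose patients without a weight, and 9.9 says BMI is not consistently recorded.
- Weight is not a listed variable.

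The text does not settle the question.

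**Step 2. Does the choice matter for a single patient?** Clearance is computed by Cockcroft-Gault, which is an assumption because the protocol names no clearance formula:

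CrCl = (140 − age) × weight / (72 × Scr), × 0.85 if female.

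CKD-EPI uses the Table S1 constants without the race term. In every example below creatinine exceeds κ, so the min term equals 1 and only the exponent −1.209 acts:

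eGFR = 141 × (Scr/κ)^−1.209 × 0.993^age, × 1.018 if female.

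| Patient | CrCl | eGFR |
|---|---|---|
| Man, 80 y, 70 kg, 1.2 mg/dL | 60 × 70 / 86.4 = 48.6 | 141 × (1.2/0.9)^−1.209 × 0.993^80 = 56.8 |
| Woman, 85 y, 55 kg, 1.0 mg/dL | 55 × 55 × 0.85 / 72 = 35.7 | 141 × (1.0/0.7)^−1.209 × 0.993^85 × 1.018 = 51.3 |
| Man, 68 y, 105 kg, 1.7 mg/dL | 72 × 105 / 122.4 = 61.8 | 141 × (1.7/0.9)^−1.209 × 0.993^68 = 40.5 |

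The first two meet the 15-49 criterion on clearance and fail it on eGFR. The third does the reverse. At a clearance of exactly 50, eGFR is 29.6 for a woman of 65 weighing 100 kg and 78.6 for a man of 80 weighing 55 kg.

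**Step 3. How common could this be?** Three cohorts of 400,000 patients were simulated. All distributions are assumed:
- 45% women.
- Mean age 70, 75 or 78 (SD 9, 10, 9).
- Mean weight 85/72, 84/71 or 80/67 kg (men/women; SD 16/15), falling 0.5 kg per year of age.
- Log-normal creatinine with median 1.0, 1.05 or 1.1 mg/dL (log SD 0.25, 0.28, 0.30), × 1.05 for men and × 0.85 for women, independent of age and weight.
- Exponents in CKD-EPI taken as negative.

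| Mean age | Meets 15-49 on CrCl | Meets 15-49 on eGFR | Missed by eGFR | Wrongly added | Rivaroxaban discordant | Apixaban discordant |
|---|---|---|---|---|---|---|
| 70 | 16.3% | 13.3% | 8.4% | 5.4% | 13.8% | 0.6% |
| 75 | 28.2% | 23.5% | 11.6% | 6.9% | 18.5% | 1.2% |
| 78 | 40.9% | 31.8% | 15.4% | 6.3% | 21.8% | 2.0% |

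Percentages are of all patients. The apixaban column applies both routes. eGFR identifies 48.5%, 58.8% and 62.3% of patients who meet the clearance criterion, so 38 to 52% of them are missed. A separate set of assumptions (age 75 ± 10, mean eGFR 60 to 72) gave about 33 to 54% missed, with 3 to 7% of all patients wrongly added. The rivaroxaban-to-apixaban ratio of discordance is 13.8/0.6 = 23, 18.5/1.2 = 15 and 21.8/2.0 = 11.

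**Step 4. Where do the errors go?** A missed patient on 15 mg moves into the inappropriate reduced-dose cell, and one on 20 mg into the appropriate standard-dose cell. A wrongly added patient moves the opposite way. Missed patients tend to be old and light, added patients heavy, so the two flows do not cancel in case mix.

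**Step 5. Below 15 mL/min.** Table S1 has a separate level for these patients, but the 15-49 criterion does not cover them. The cells in 9.7(a) are only criterion present or absent, and no rule says where these patients go.

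**The case against.** The strongest reply is that Table S1 defines subpopulations, so CKD-EPI there serves the renal subgroup. On this view 9.7(a), taken at its word, already classifies dose by the clearance-based criteria. Section 9.7(b) does name clearance and serum creatinine, serum creatinine is extracted, and a clearance formula with a weight rule could sit in a statistical analysis plan that is not shown. Much of this stands. Nowhere does the protocol say that CKD-EPI decides the dose class, and CKD-EPI is not the only renal measure it mentions; it is the only one with a formula. The reply does not remove the conflict: 9.7(b) puts CKD-EPI and clearance in one phrase, and the missing-data expectation fits eGFR.

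Three stronger readings are tempting, and the documents do not support them:
- **That the error runs one way and simply inflates rivaroxaban under-dosing.** The 68-year-old man and the wrongly-added column show otherwise. The net bias in the odds ratios is not established.
- **That one can state what share of the inappropriate 15 mg cell truly meets the criterion.** This would need the 10% in section 7 to be a clearance-based rate. It comes from an unpublished study whose renal measure is not given.
- **That the Table S1 formula is itself wrong in its signs or exponents.** Superscripts and a minus sign may have been lost in text extraction; only the source PDF can show it.

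Nor does the protocol assign patients below 15 mL/min to the criterion-absent cells. It leaves them unassigned, and some apixaban users among them could still qualify by the first route.

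**Conclusion.** The concern holds as an unresolved conflict in how the primary exposure is built. The criterion is stated in one renal measure, the only formula is for another, the cut-points of the first are applied to the second, and the weight needed for the first (and for apixaban's first route) is not listed. Misclassification is conditional: it arises if eGFR stands in for clearance. Rivaroxaban classification would then be discordant in roughly 14 to 22% of patients in the assumed cohorts, with missed patients outnumbering those wrongly added, against roughly 1 to 2% for apixaban. These percentages rest on Cockcroft-Gault and on assumed age, weight and creatinine distributions, and are not predictions for this database. The imbalance between drugs follows from the structure of the criteria and was present in every cohort tried. The conflict should be resolved before the exposure is programmed.

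**What to change.** Reconcile 9.3.1.2, 9.3.3, 9.7 and Table S1 so that one named measure decides the dose class. This concerns analytic classification only, not how patients should be dosed.

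1. In 9.3.3 and 9.7(a), define creatinine clearance with its formula (for example Cockcroft-Gault from age, sex, weight and serum creatinine), and use it wherever 9.3.1.2 states the criterion in clearance.
2. Add body weight to the covariate list, with a look-back rule and a rule for missing values. Restate the expected proportion excluded, since the under-5% figure refers to eGFR.
3. Keep CKD-EPI for the renal subgroup, and repeat the dose classification with it as a sensitivity analysis. Reword 9.7(b) so that the two measures are not presented as one.
4. State how patients below 15 mL/min are handled in the dose-by-criterion cells.
5. Add the choice of renal measure to the limitations in 9.9.

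The cost is protocol wording and programming; creatinine is already extracted and weight is already needed for apixaban. The downside is that some patients without a recorded weight drop out of this classification.

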9.1 Study design

This is a population-based retrospective cohort study with a nested case-control analysis to assess safety and effectiveness of new users of rivaroxaban and apixaban versus new users of warfarin in a cohort of NVAF patients from THIN database (secondary data) in the UK.

All patients aged 18 and above and who have been enrolled in the databases for at least 1 year and had their first prescription recorded in the databases at least 1 year ago will be included in source population. A patient will be considered eligible to enter a study cohort as a new-user of one of the three study drugs when he or she has a first prescription of the index drug recorded during the enrollment period. Individuals meeting the criteria of new user of more than one study drug during the enrollment period will be assigned to the study cohort with the earliest start date. Among the three study cohorts, we will further identify patients with Non-valvular Atrial Fibrillation (NVAF) defined as: Patients with a record of Atrial fibrillation (AF) any time prior start date or within the 2 weeks after the start date, and free of valvular replacement or mitral stenosis prior to start date or 2 weeks after start date.

Additionally, NVAF patients with other recent indications of OAC initiation will be excluded. Thus patients with an entry of venous thromboembolism or orthopedic arthroplasty recorded in the last 3 months before the date of first time use of OAC or in the week after the start date will be excluded from the study cohort. Individuals on more than one OAC on the start date will also be excluded.

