9.3.2.1 Validation of outcomes

Anonymized free text will be obtained for all individuals experiencing safety or effectiveness events (as defined above) during the study period. We will manually review their clinical profiles with available free text to confirm or discard these events. Since the study cohort will include individuals with a history of ischemic and/or hemorrhagic events before the study period, this manual review of clinical profiles would be essential to discard diagnosis recorded during the study period that actually refer to episodes that occurred before start date. Furthermore, only events that required

hospitalization will be considered. For this process of validation of the outcomes, all patient personal identifiers will be suppressed and information on drug use removed to allow for a blinded revision of patient profiles. Additionally we will obtain anonymized free text from a random sample of individuals (n=100) that allegedly do not experience safety or effectiveness events (i.e. no event codes recorded). We will manually review their clinical profiles with available free text to identify any signs of safety or effectiveness events (meeting our operational definition) that had not been identified through the code search.

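### Table S3 contradicts the protocol's own NVAF definition: three of its 24 AF entry codes name paroxysmal atrial or supraventricular tachycardia, and any one of them alone qualifies a patient

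*Protocol*

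**What the plan says.** Protocol section 9.1 defines an NVAF patient by "Patients with a record of Atrial fibrillation (AF) any time prior start date or within the 2 weeks after the start date", together with freedom from valve replacement and mitral stenosis. Table S1 in Annex 3 gives the same rule with a different anchor date: "Patients with a record of Atrial fibrillation (AF) any time prior index date or within the 2 weeks after the index date". Neither text names any rhythm other than atrial fibrillation.

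The rule is put into practice by the list headed "Table S3- AF READ codes". Besides the fibrillation and flutter codes it contains:

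- 3274.00, "Ecg: paroxysmal atrial tachy"
- G570.00, "Paroxysmal supraventricular tachycardia"
- G570000, "Paroxysmal atrial tachycardia"

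The exclusion for other anticoagulant indications in section 9.1 covers "venous thromboembolism or orthopedic arthroplasty recorded in the last 3 months before the date of first time use of OAC". Such an entry up to seven days following treatment start also excludes the patient. Section 9.3.2.1 describes the only manual record review: "Anonymized free text will be obtained for all individuals experiencing safety or effectiveness events (as defined above) during the study period", plus 100 people without event codes, who are searched for missed events.

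**The concern.** A patient whose only qualifying record is one of the three tachycardia codes meets the NVAF criterion as programmed but not as defined. The entry rule has no look-back limit and asks for no second or confirming code, so one old entry suffices.

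What is at stake is mainly the primary exposure. The primary objectives in section 8.1 compare appropriate and inappropriate dosing by the label for stroke prevention in AF, and the criteria in section 9.3.1.2 are framed for NVAF. If a patient has no AF and takes the drug for another reason, the algorithm still assigns a dose class, but the class answers a question that does not apply to that patient. Section 7 itself notes that rivaroxaban is also indicated for treatment and prevention of VTE.

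This is not a detail left to a later document, because the protocol fixes the code list itself.

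**Working it through.** **1. The list against the definition.** Table S3 has 24 codes. Three name only atrial or supraventricular tachycardia (3274.00, G570.00, G570000). Two name flutter only (3273.00, G573100). The other 24 − 3 − 2 = 19 name atrial fibrillation. So 3/24 = 12.5% of the codes name neither fibrillation nor flutter. This is a share of codes, not of patients.

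**2. Would a later rule remove these patients?**

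- Confirming code: none is required.
- Valve exclusions (Tables S4 and S5): they do not concern rhythm.
- Other indications: only recent VTE and arthroplasty are excluded. An older VTE or any other indication passes this rule.
- Manual review: it concerns outcome events, and the AF diagnosis is not within its scope.

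None of these rules removes a patient for lacking an AF record.

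**3. Planned figures used for scale (section 9.5).** With 10,000 initiators per drug, N = 30,000. The expected 1800 ischaemic strokes at 2% a year are reproduced by 30,000 × 0.02 × 3 = 1800. The three-year mean follow-up is implied, not stated. The same factor gives 900 and 3600 for the other two outcomes.

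**4. Possible size with equal shares across drugs.** The protocol gives no share, so these inputs are assumptions: a share f = 1% to 10% enters on the three codes alone (300 to 3,000 of 30,000), their stroke rate is k = 0.25 to 1 times the AF rate, and their true rate ratio is 1.

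Weight of AF patients: w = (1 − f) / [(1 − f) + f·k]. Observed ratio = RR·w + (1 − w).

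| f | k | w | RR 1.3 reads | RR 1.8 reads | Expected strokes |
|---|---|---|---|---|---|
| 0.01 | 0.25 | 0.9975 | 1.299 | 1.798 | 1786 |
| 0.05 | 0.25 | 0.987 | 1.296 | 1.790 | 1732 |
| 0.10 | 0.25 | 0.973 | 1.292 | 1.778 | 1665 |
| 0.10 | 1.0 | 0.900 | 1.270 | 1.720 | 1800 |

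The ratios 1.3 and 1.8 are the detectable odds ratios that section 9.5 gives for ischaemic stroke: overall, and for inappropriate reduced-dose apixaban against warfarin.

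**5. Possible size with unequal shares.** Take f = 1% to 5% in one cohort only, k = 0.25 and a true ratio of 1.00. The rate in that cohort falls by f × 0.75, which is 0.75% to 3.75%.

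- All in warfarin: 1/0.9925 = 1.008 to 1/0.9625 = 1.039.
- All in the NOAC cohort: 0.9925 to 0.9625.
- Equal shares: 1.00.

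The sign depends entirely on a split that the protocol does not report.

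**6. Small dose cells.** On the assumptions of section 9.5, the inappropriate reduced-dose apixaban group is 10,000 × 0.5 × 0.3 × 0.5 = 750 people. A share of 1% to 10%, spread evenly, would be about 8 to 75 of them.

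**The case against.** The case for leaving the list alone has real force.

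- **The documents show that such patients can enter, not that they do.** Entry also requires starting an oral anticoagulant and having no recent VTE, arthroplasty, valve replacement or mitral stenosis. Some patients with only a tachycardia code may have AF that was never coded. This stands: a reader might infer that the cohort demonstrably contains patients without AF, and the protocol does not support that.
- **The VTE route is narrow.** The three-month window runs back from first anticoagulant use, so a naïve patient treated soon after a VTE is excluded. Section 9.2.3 also drops NOAC users outside the listed daily doses, and rule 3B in section 9.3.1.1 can assign some rivaroxaban 15 mg prescriptions two tablets a day (30 mg), which is outside them. This narrows the route but does not close it.
- **Stroke can still be observed.** A reader might infer that the stroke endpoint does not apply to these patients. It does, since strokes in them can be counted. Only the meaning of the label-based dose class is in doubt.
- **The direction of bias is unknown.** A reader might infer that NOAC odds ratios are pushed upwards. That needs these patients to be concentrated among warfarin starters, and nothing in the protocol says so.
- **Adjustment may absorb part of any risk difference.** The model in section 9.7 includes the stroke-risk scores, prior stroke, frailty and comorbidity. That is fair for baseline risk, but adjustment cannot give meaning to a dose class in a patient without the indication.
- **Section 9.1 read literally excludes flutter as well.** This is correct, and the definition should settle it.

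None of this reconciles the list with the definition.

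**Conclusion.** The point holds as an inconsistency in the population definition. Section 9.1 and Table S1 require atrial fibrillation, Table S3 accepts three codes for other tachycardias, and nothing later verifies the diagnosis. The consequence that can be supported is limited: an unknown number of patients may fall outside the NVAF stroke-prevention population, and their appropriate or inappropriate dose class may not be meaningful.

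The numerical effect is probably small. On the assumed shares and stroke rates above, 1.3 reads no lower than 1.27 with equal shares, and a null ratio moves only to between about 0.96 and 1.04 with fully one-sided shares of up to 5%. These are crude illustrations. A larger share, or concentration in one of the small dose cells, would matter more. The reason to correct the list is that entry should match the stated definition, not that a large or directional bias has been shown.

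**What to change.** Delete 3274.00, G570.00 and G570000 from Table S3. Alternatively, keep them but require an additional AF or flutter code for patients who have only these. Patients who also carry an AF code stay in under either option.

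Report, for each drug cohort, how many patients qualify on the three codes alone. State in section 9.1 and Table S1 that atrial flutter qualifies, if that is intended.

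Before extraction this is an edit of three lines plus one count. After extraction it would mean rebuilding the cohorts and resampling the controls. The price is a slightly smaller cohort and the possible loss of a few true AF patients who were loosely coded; the reported counts will show how large the affected group is.
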